2. OBJECTIVES

PRIMARY OBJECTIVES:

- Document the efficacy of the CyberKnife® procedure, where efficacy is defined by biochemical Disease-Free Survival (bDFS), using Phoenix and ASTRO definitions, at 5 years.

- Compare the CyberKnife® Stereotactic Radiosurgery System bDFS rate to published HDR monotherapy bDFS rates reported in the literature.

SECONDARY OBJECTIVES:

- Measure rates of acute and late grade 3-5 gastrointestinal and genitourinary toxicity observed during the five years following CyberKnife® Stereotactic Radiosurgery System for prostate cancer. Acute toxicity will be defined as occurring within 90 days from completion of treatment. Late toxicity will be defined as occurring more than 90 days from completion of treatment. It is graded based upon Common Terminology Criteria for Adverse Events (CTCAE), v3.0 and RTOG/ECOG definitions (see appendix 5).
- Measure rates of local failure, distant failure, clinical disease-free survival, disease-specific survival, and overall survival
- Examine Quality of Life (QOL) in generic and organ-specific domains

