8. TREATMENT: CYBERKNIFE® RADIOSURGERY

- 8.1. Intermediate risk patients will be treated with either: CyberKnife® SBRT boost of 21 Gy (7 Gy X 3) followed by prostate/SV IMRT 45-50.4 Gy (treatment planning and delivery per current standards of care); or CyberKnife® SBRT monotherapy 36.35Gy (7.27Gy x 5). Short term Androgen Deprivation Therapy (4-6 months per standards of care) is strongly recommended for all intermediate risk patients.

High risk patients will be treated with CyberKnife® boost of 21 Gy (7 Gy X 3) followed by whole pelvis IMRT 45-50.4 Gy (treatment planning and delivery per current standards of care). Short or long term ADT (6 months up to 3 years per current standards of care) is strongly recommended for high risk patients.

Standards of care are based on National Comprehensive Cancer Network guidelines. Per investigator decision and patient discussion, the appropriate treatment plan will be determined for each patient based on their risk group outlined by these guidelines. Patient age, performance status, medical comorbidities, Gleason score and other disease features (Gleason score 4+3 vs. 3+4) will be taken into consideration. Strong recommendation is made for consideration of combined modality therapy for patients with : Gleason score 4+3 disease, more than 50% positive cores, and/or PSA velocity of more than 2ng/ml in the year preceding tissue diagnosis, given survival benefit of short term ADT. CyberKnife® SBRT monotherapy would typically be appropriate only for low volume GS 3+4 disease with no other adverse features.

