11. STATISTICAL CONSIDERATIONS

11.1. DATA ANALYSIS AND SAMPLE SIZE CALCULATION

Response rates with 95% confidence intervals and one-sample Kaplan-Meier analysis will be performed to show 5 year disease free survival and overall survival for patients treated with CyberKnife® SBRT monotherapy and patients treated with whole pelvis IMRT and ADT per current standards of care, followed by CyberKnife® SBRT boost.

In treatment groups, toxicity, rates of local failure, distant failure, clinical disease-free survival, disease-specific survival, and overall survival; quality of life (QOL) in generic and organ-specific domains will be reported descriptively for the samples. In addition descriptive statistics will be provided comparing the CyberKnife® Stereotactic Radiosurgery System bDFS rate to published HDR monotherapy bDFS rates reported in the literature for each group.

Investigators expect that overall, patients treated with CyberKnife® SBRT monotherapy will have a 5 year PSA DFS rate of $80\% \pm 0.15$ (total width = .30) using a confidence level of 95%, a required sample size of 32 subjects is necessary.

Investigators expect that overall, patients treated with whole pelvis IMRT and ADT per current standards of care, followed by CyberKnife® SBRT boost will have a 5 year PSA DFS rate of $70\% \pm 0.15$ (total width = .30) using a confidence level of 95%, a required sample size of 40 subjects is necessary.

It is expected that up to 150 subjects will be enrolled at this site.

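### The plan recommends ADT for SBRT monotherapy men but pools their bDFS regardless of ADT, so the HDR monotherapy comparison cannot separate a CyberKnife effect from an ADT effect

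*Combined protocol and SAP*

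**What the plan says.** The second primary objective in section 2 is: "Compare the CyberKnife® Stereotactic Radiosurgery System bDFS rate to published HDR monotherapy bDFS rates reported in the literature". The first defines efficacy of the CyberKnife procedure as 5-year bDFS.

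Section 8.1 gives intermediate-risk men one of two regimens: a three-fraction boost with IMRT, or five-fraction SBRT monotherapy. On hormones it states: "Short term Androgen Deprivation Therapy (4-6 months per standards of care) is strongly recommended for all intermediate risk patients". It makes no exception for monotherapy. Further down, it urges combined modality therapy for men with adverse features, "given survival benefit of short term ADT", and adds that "SBRT monotherapy would typically be appropriate only for low volume GS 3+4 disease with no other adverse features".

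Section 11.1 describes its two groups differently. The boost group is defined as receiving pelvic IMRT and ADT. The other is called simply CyberKnife SBRT monotherapy, with one expected rate of 80% ± 15 points and the statement "using a confidence level of 95%, a required sample size of 32 subjects is necessary". For the comparator, and with reference to these two groups, "descriptive statistics will be provided comparing the CyberKnife® Stereotactic Radiosurgery System bDFS rate to published HDR monotherapy bDFS rates reported in the literature for each". No breakdown, adjustment or sensitivity analysis by ADT is planned.

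Table 1 lists the HDR monotherapy series without ADT use. The text after it gives 82% as the projected 5-year ASTRO-definition rate for intermediate-prognosis HDR cases.

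**The concern.** The monotherapy group is the only one treated without added IMRT, so it is the natural match for HDR monotherapy. Under section 8.1 it may contain men treated with SBRT alone and men treated with SBRT plus 4-6 months of ADT, in proportions set by investigator and patient choice. The protocol itself credits short-term ADT with a survival benefit. It measures bDFS from enrollment (section 9.4), so time on ADT counts as disease-free time.

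A single pooled rate from such a group describes a treatment policy, not the device. Set beside HDR series whose ADT use is not stated, it leaves a reader unable to tell whether a difference, or the absence of one, comes from CyberKnife or from ADT. That weakens a primary objective, although the comparison is descriptive and no test, margin or decision rule depends on it.

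**Working it through.** **1. The plan's own sample size.** The target is a two-sided 95% interval of total width at most 0.30 for one proportion. The smallest n by the exact (Clopper-Pearson) method is 32 at 80% (width 0.2985) and 40 at 70% (width 0.2997). The continuity-corrected Wilson interval gives the same two numbers. Both stated figures reproduce, and ADT does not enter the calculation.

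**2. The HDR benchmark.** Table 1 gives 89% at 3 years for the intermediate-risk HDR series. Projected at a constant failure rate, 0.89^(5/3) = 0.823, which matches the stated 82%. The gap to the planned monotherapy rate is 82 − 80 = 2 points, with CyberKnife the lower.

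**3. How far ADT could move the pooled rate.** The documents give neither uptake nor effect size, so these inputs are assumptions:

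- rate without ADT S0 = 0.80 (borrowing the figure in 11.1, which does not say what background treatment it assumes)
- hazard ratio for PSA failure with ADT: 0.5 to 0.8
- uptake u: 25% to 100%

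Pooled rate = u × S0^HR + (1 − u) × S0, so the shift is u × (S0^HR − S0).

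With ADT, 0.80^0.5 = 0.894, 0.80^0.65 = 0.865 and 0.80^0.8 = 0.837.

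| Uptake | HR 0.5 | HR 0.65 | HR 0.8 |
|---|---|---|---|
| 25% | +2.4 | +1.6 | +0.9 |
| 50% | +4.7 | +3.2 | +1.8 |
| 75% | +7.1 | +4.9 | +2.7 |
| 100% | +9.4 | +6.5 | +3.7 |

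Shifts are in percentage points. They run from 0.9 to 9.4, and nine of the twelve exceed the 2-point gap in step 2. All lie inside the planned ±15 points, so the pooled interval could not reveal them. If the 80% already includes ADT users, the table does not apply as it stands.

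**4. Precision if the rate is split by ADT.** At 50% uptake, 32 men give 16 per stratum, and the exact half-width at 80% is about ±21 points instead of ±15. As an example, 13/16 (81%) has an exact 95% interval of 54% to 96%. To keep 32 men in each stratum, the monotherapy group would need 32/0.50 = 64 men at 50% uptake, or 32/0.25 = 128 at 25% or 75%. Planned enrollment is up to 150 across all groups.

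**The case against.** **Section 11.1 never says that the monotherapy men are free of ADT.** This is correct. A reader might infer that the plan sizes and analyses the group as though no ADT were given, but that comes only from 11.1's silence. What stands is that ADT status is left undefined.

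**Uptake may be low.** Section 8.1 links combined modality therapy to the ADT benefit and reserves monotherapy for low-volume, favourable Gleason 3+4 disease. That can be read as meaning that monotherapy men often go without ADT. It sits uneasily with a recommendation for all intermediate-risk men, and the two statements should be reconciled. Until then uptake is unknown, which is why the range starts at 25%.

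**No bias in favour of CyberKnife is shown.** This also stands. A reader might infer that ADT flatters the device. That requires the HDR series to have used less ADT, which the documents do not say; with similar or greater use the bias would vanish or reverse. In addition, a PSA rise after ADT stops, measured from a low reached on ADT, could itself meet a failure definition.

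**There may be no advantage to explain.** A reader might set the 85-90% predicted for intermediate-risk men in the background against 82% and conclude that ADT could account for the whole 3-8 point difference. The 85-90% rests on HDR boost data and covers all intermediate-risk men. For monotherapy, 11.1 expects 80%, which is below 82%.

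**Strata chosen by physicians do not isolate the device.** This is true: men with and without ADT will differ in prognosis. Stratified reporting makes the mixture visible but does not remove confounding.

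**Conclusion.** The concern holds as a limit on interpretation. Followed as written, the plan cannot separate a CyberKnife effect from an ADT effect in the comparison with HDR monotherapy, which is a primary objective. The direction of any bias is unknown. The 0.9 to 9.4 point range depends entirely on the assumed hazard ratio, uptake and no-ADT rate. It shows only that a plausible ADT contribution could be larger than the 2-point gap between the planned 80% and the 82% benchmark.

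It is not a sizing error: N=32 reproduces, and no type I error or power figure is involved. The case report forms in Appendix IV are not shown and may already capture ADT. The section 9 assessment schedule does not list it, and the only ADT status item found is a baseline question in the eligibility checklist. Nothing here bears on whether ADT should be given.

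**What to change.** In section 11.1:

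- Report 5-year bDFS in the SBRT monotherapy group (Kaplan-Meier, 95% CI) overall and separately for men with and without planned ADT, with the number in each. Call the split descriptive.
- Record ADT use and duration, if the case report forms do not already do so.
- Add ADT use to the HDR comparator table for each cited series that reports it, and compare like with like where possible.
- Where a series does not report it, label the result as CyberKnife with or without ADT, and do not attribute a difference from HDR to the device.
- State that the 80% / N=32 calculation covers men with or without ADT.

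The cost is a few sentences of analysis text, possibly one or two data items, and a re-reading of publications already cited, some of which may not report ADT. The main downside is small strata with wide intervals (54% to 96% in the 13/16 example), so the overall rate should stay beside them. Neither the sample size nor treatment needs to change for this.

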8.4.2. QUALITY ASSURANCE

8.4.2.1. BENCHMARK (DRY RUN) CASE REVIEW: A treatment plan shall be developed, and the plan reviewed by the PI and Physics Chair; completion of a satisfactory plan is required prior to patient enrollment.

8.4.3. EVALUATED STRUCTURES:

8.4.3.1. CTV: The Clinical Treatment Volume (CTV)

8.4.3.1.1. The CTV is the pre-registered MRI defined prostate volume, unless MRI-based imaging is medically contraindicated or judged inaccurate by the investigator (see section 8.3.3.1.2.), in which case the CT may be used to define the CTV. Additionally, at the discretion of the investigator, some or all of the adjacent seminal vesicle volume may be included in the CTV for any of the following reasons: prostate base involvement by any criteria, perineural invasion, or equivocal MRI evidence of seminal vesicle invasion in a patient with no other clinical or pathological evidence for seminal vesicle invasion, and/or intermediate or high risk disease.

8.4.3.2. PTV: The prescription dose shall be delivered to the Planning Tumor Volume (PTV).

8.4.3.2.1. The PTV is an enlargement of the CTV. The CTV should be expanded to include a 2-5 mm margin at the proximal, distal, anterior, lateral and generally less in the posterior aspects of the CTV. Posteriorly, where the CTV abuts the rectum, there will be no margin.

8.4.3.3. NORMAL TISSUES: CONTOURING REQUIRED: The structures listed below will be contoured and evaluated with DVH analysis. Bowel peristalsis and bladder filling change the size and location of normal structures. If the CT and MRI show normal tissues in different locations immediately adjacent (i.e., within < 2cm) the prostate, the contoured

structure shall be a larger composite of both image sets. Grid size should be sufficiently large to include the entire structure.

- 8.4.3.1. **RECTUM:** defined as a solid organ (not the wall), extending from 1.5 cm superior to 1.5 cm inferior to PTV.
- 8.4.3.2. **BLADDER,** defined as a solid structure including the bladder wall and lumen.
- 8.4.3.3. **URETHRA:** To be defined on CT more so than MRI. Approval by the Radiation Oncologist is required.
- 8.4.3.4. **PENILE BULB:** Will be defined only if a co-registered MRI is used in the planning process. The penile bulb is defined as the portion of the bulbous spongiosum that lies inferior to the urogenital diaphragm.
- 8.4.3.5. **SIGMOID COLON OR OTHER BOWEL** lying within 2 cm of the PTV should be contoured.
- 8.4.3.6. **PENIS AND TESTICLES:** The region of the penis and testicles shall be contoured with enough margin to allow for day-to-day changes in their positioning.

8.4.4. **DOSE SPECIFICATIONS:** All specified doses are for the entire treatment course. All volume percentages are rounded to the nearest tenth of a percent for consistency, i.e. a volume of 0.02% shall be recorded as 0.0%.

8.4.4.1. The **PRESCRIPTION DOSE** of 36.25Gy in 5 fractions for monotherapy or 21Gy in 3 fractions for boost will be delivered in <10 days, with > 95% of the PTV encompassed within the prescription isodose volume. Maximum PTV dose 130% prescription dose.

8.4.4.2. **CONFORMALITY INDEX FOR NORMAL TISSUES:** The ratio of the prescription isodose volume to the PTV will be ≥ 1.0 and ≤ 1.5 . Minor variation: ≤ 0.99 or $\geq 1.51 - 2.0$

8.4.4.3. **DOSE OBJECTIVES:** The following table outlines the target and normal tissue objectives:

Organ	Constraint	21Gy in 3Fx	36.25Gy in 5 Fx
PTV	Dose Normalization	70 - 80%	70 - 80%
PTV	Dose min 95%	≥ 21 Gy	≥ 36.25 Gy
PTV	Dose Max	26.25 - 30 Gy	45.31 - 51.79 Gy
Prostate	Dose Min to 100%	≥ 21 Gy	≥ 36.25 Gy
Rectum	Dose Max to 1 cc	≤ 22.05 Gy	≤ 38.06 Gy
Rectum	3 cc	≤ 19.95 Gy	≤ 34.4 Gy
Rectum	10%	≤ 18.9 Gy	≤ 32.625 Gy
Rectum	20%	≤ 16.8 Gy	≤ 29 Gy
Rectum	50%	≤ 10.5 Gy	≤ 18.125 Gy

Bladder	Dose Max to 1 cc	<= 22.05 Gy	<= 38.06 Gy
Bladder	10%	<= 18.9 Gy	<= 32.625 Gy
Bladder	50%	<= 10.5 Gy	<= 18.125 Gy
Penile Bulb	Dose Max to 1 cc	<= 21 Gy	<= 36.25 Gy
Penile Bulb	3 cc	<= 11.34 Gy	<= 20 Gy
Femoral Heads	Dose Max to 1 cc	<= 17.01 Gy	<= 30 Gy
Femoral Heads	10 cc	<= 11.34 Gy	<= 20 Gy
Urethra	Dose Max to 0.03 cc	<= 22.5 Gy	<= 38.78 Gy
Bowel	20 cc	<= 24 Gy	<= 25 Gy
Penis/Testicles	1 cc	as low as possible	as low as possible

8.4.4.4.

8.5. CYBERKNIFE® TREATMENT DELIVERY

8.5.1. The prescribed PTV dose shall be given using the CyberKnife®

8.5.2. Bowel/bladder preparation:

8.5.2.1. The rectum will be emptied of its contents by use of one or more Fleets enemas prior to the planning CT and MRI scans.

8.5.2.2. To improve comfort and minimize inconvenience to the patient, if possible, the CT and MRI planning studies will be done consecutively.

8.5.3. Treatment should be completed within 7 days.

8.5.4. At least three fiducials should be identified for each treatment. If fewer than three fiducials can be tracked, then additional fiducials will be placed, and the patient replanned. Every effort will be made to treat using rotational corrections. The treatment system will be set to record rotations on the treatment printout. On a given treatment, if rotational corrections are not possible, treatment may continue, with rotational deltas recorded, as long as these remain below 2 degrees. For subsequent treatments, diet changes or additional bowel preparations will be made, and/or rectal tube placed, and treatment shall be attempted using rotational corrections. If treatment proceeds without rotational corrections, the therapist shall inform the attending radiation oncologist, and record the duration of treatment performed without rotations.

8.5.5. On the day of the CyberKnife® treatment, the patient will be taken into the CyberKnife® system treatment room, set up in their respective immobilization devices and positioned on the CyberKnife® couch. X-rays will be taken with the CyberKnife® system to ensure that the tumor is aligned in a manner consistent with the position in which the treatment plan CT image was taken. Target movement is expected to require imaging every 1-3 nodes, per the discretion of the attending physician, and in no situation should imaging occur less frequently than every 5 nodes. Fiducial locations in the images will be extracted and compared to the fiducial locations in the CT scans to estimate target movements. The following planning and treatment information shall be recorded for every plan and fraction delivered: set-up

time required, number of nodes treated, number of nodes treated with rotational corrections, number of nodes imaged, and total treatment time. This data will be collected onto Case Report Forms.

8.5.6. All planned nodes will be treated whenever possible. If treatment must be terminated prematurely on fractions 1-3, compensate as follows. If 2/3 or more of all non-zero nodes were treated, then the untreated nodes plus the full next fraction should be treated on the next treatment day (this should introduce an error of < 5% in BED delivered). If less than 2/3 of the non-zero nodes were treated, then the untreated portion of this fraction (only) will be made up for on the following day. The subsequent fraction shall be delivered on the next treatment day. If treatment must be terminated prematurely on the fourth fraction, and 90% of the non-zero nodes were treated, then no further treatment shall be given (this should introduce an error of < 5% for total BED delivered). If fewer than 90% of the non-zero nodes were treated, then the deficit shall be delivered on the following treatment day. All such variations shall be recorded.

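### Section 8.5.6 numbers its interrupted-fraction rule for a four-fraction course, but the trial gives three or five fractions; separately, Section 8.4.4 gives two different ceilings for the PTV dose

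*Combined protocol and SAP*

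**What the plan says.** **Courses.** Section 8.4.4.1 prescribes "36.25Gy in 5 fractions for monotherapy or 21Gy in 3 fractions for boost". Section 8.1 agrees on the fraction counts and always pairs the boost with IMRT; for intermediate risk it specifies "CyberKnife® SBRT boost of 21 Gy (7 Gy X 3) followed by prostate/SV IMRT 45-50.4 Gy". Section 8.1 gives the monotherapy dose as 36.35 Gy (7.27 Gy x 5), slightly different from 8.4.4.1.

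**Interrupted fractions (Section 8.5.6).** The default is "All planned nodes will be treated whenever possible". Two specific rules follow.

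- Early fractions: "If treatment must be terminated prematurely on fractions 1-3, compensate as follows". If at least 2/3 of the non-zero nodes were treated, "the untreated nodes plus the full next fraction should be treated on the next treatment day". If fewer were treated, "the untreated portion of this fraction (only) will be made up for on the following day".
- Fourth fraction: if it is "terminated prematurely on the fourth fraction, and 90% of the non-zero nodes were treated, then no further treatment shall be given". The protocol adds that "this should introduce an error of < 5% for total BED delivered". Below 90%, the deficit is given on the following treatment day.

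All such variations are to be recorded. Section 8.5.3 asks for completion within 7 days, and 8.4.4.1 for delivery in under 10 days.

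**PTV maximum.** Section 8.4.4.1 sets 130% of the prescription dose. The table in 8.4.4.3 lists normalization of 70-80% and PTV maxima of 26.25-30 Gy (boost) and 45.31-51.79 Gy (monotherapy).

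**The concern.** The rule in 8.5.6 has a sound structure: carry a small deficit forward while fractions remain, and use a separate rule at the last one. It takes fraction 4 as the last, which fits neither course.

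Staff dealing with an interrupted final fraction therefore find wording that does not apply (boost) or no specific rule (monotherapy). Similar interruptions may then be handled differently, and it is unclear what counts as a variation to be recorded.

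The two PTV ceilings raise the same kind of problem in planning. A plan with a maximum between 130% and 142.9% of prescription satisfies the table and breaches the text, and the protocol does not say which of them decides.

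**Working it through.** **1. Rule against courses**

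| Fraction | Boost, 3 x 7 Gy | Monotherapy, 5 x 7.25 Gy |
|---|---|---|
| 1-2 | carry-over; works | carry-over; works |
| 3 | carry-over, but no next fraction exists | carry-over; works |
| 4 | does not exist | 90% stop rule, though not the last fraction |
| 5 | does not exist | general default only |

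So one of three boost fractions has a branch with no target, and one of five monotherapy fractions has no specific rule. The only four-fraction schedule in the documents is a cited HDR brachytherapy series (9.5 Gy x 4, Tables 1 and 2), which is not a trial treatment.

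**2. The stated BED tolerance**

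BED = sum of d(1 + d/(α/β)), with α/β = 1.5 Gy from Section 1.7. Assumptions: one interruption, exactly at the rule's threshold, with share of nodes taken as share of dose.

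- Full courses: 21 x (1 + 7/1.5) = 119.0; 36.25 x (1 + 7.25/1.5) = 211.46.
- Monotherapy, 2/3 carry-over (4.833 and 9.667 Gy): +3.7%. Monotherapy, 90% stop on one fraction: -3.5%.
- Boost alone, carry-over (7, 4.667, 9.333 Gy): +7.26 units, 7.26/119 = +6.1%. Boost alone, 90% stop on the last fraction: -6.91 units, 6.91/119 = -5.8%.
- Boost plus IMRT, assuming 1.8 Gy per IMRT fraction: IMRT BED is 45 x 2.2 = 99.0 or 50.4 x 2.2 = 110.88. Carry-over is 7.26/218.0 = +3.3% or 7.26/229.88 = +3.2%. The stop is -3.2% or -3.0%.
- Bound with no assumption on IMRT fraction size: IMRT BED exceeds 45, so the errors are at most 7.26/164 = 4.4% and 6.91/164 = 4.2%.

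At α/β = 3 (an assumed alternative), monotherapy gives +3.1% and -3.3%, and boost plus IMRT at most +3.2% and -3.3%. The tolerance of under 5% therefore holds for both courses when IMRT is counted, and would still hold if the rule were moved to each course's true last fraction.

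**3. PTV maximum**

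The table reproduces exactly as prescription divided by normalization:

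- 21/0.80 = 26.25 and 21/0.70 = 30.0 Gy.
- 36.25/0.80 = 45.31 and 36.25/0.70 = 51.79 Gy.

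This is 1/0.80 = 125% to 1/0.70 = 142.9% of prescription. The text cap gives 1.3 x 21 = 27.3 Gy and 1.3 x 36.25 = 47.1 Gy. The table exceeds it by up to 30 - 27.3 = 2.7 Gy and 51.79 - 47.1 = 4.7 Gy. Both limits are met only when normalization is at least 1/1.3 = 76.9%, so about 6.9 of the table's 10 percentage points lie outside the cap.

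**4. Monotherapy dose**

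36.35/36.25 = 1.003, a 0.3% difference. The table in 8.4.4.3 uses 36.25 Gy, as 8.4.4.1 does.

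**The case against.** Much can be said for the protocol, and most of it limits the point without removing it.

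- **Boost fraction 3 can still be completed.** The untreated nodes can be given on the next treatment day; only the reference to a further full fraction has no object. The branch for less than 2/3 also makes up the deficit the following day. This stands: the wording is defective, but a workable action remains.
- **Monotherapy fraction 5 is not uncovered.** The default to treat all nodes applies, and the 7-day and under-10-day windows bound any make-up. This also stands. What is missing is a stop threshold and a stated make-up day.
- **The PTV limits overlap.** Normalization of about 77-80% satisfies both. Section 8.4.4.3 is headed as objectives, so a careful planner might apply the stricter text. But the table's own column is headed as constraints, and no priority is stated.
- **Part of the remedy is clinical choice.** Extending carry-over to monotherapy fraction 4 follows the existing structure but is not dictated by the text. Nor do the documents support raising the cap to 142.9% in preference to keeping 130%.

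A reader might infer that monotherapy patients interrupted on fraction 4 would lose fraction 5. That would deliver 3.9 x 7.25 = 28.275 of 36.25 Gy, or 22% less dose. The text does not support this as the intended meaning: the stop rule's own tolerance is under 5% of total BED, which fits only forgoing the rest of that one fraction. The wording still invites the misreading.

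A reader might also infer from the boost-alone figures (+6.1%, -5.8%) that the tolerance is wrong. It is not: the stop rule speaks of total BED, Section 8.1 always adds IMRT, and as written the stop rule never reaches the boost.

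**Conclusion.** The point holds as an internal inconsistency and is minor. Section 8.5.6 is wrong as written for both courses, because it places the final-fraction rule on a fraction that is final in neither. The PTV ceilings conflict over the upper part of the table, by up to 2.7 Gy (boost) and 4.7 Gy (monotherapy). The 36.35 Gy entry in Section 8.1 is clerical.

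Nothing is miscalculated: the table reproduces, and the BED tolerance holds under the stated assumptions. The numbering and PTV conflicts follow from the text alone; only the BED percentages depend on α/β, on equating node share with dose share and, for the narrower boost range, on 1.8 Gy IMRT fractions.

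The documents give neither the frequency of interrupted fractions nor the number of plans above 130%, so the practical reach cannot be sized. It would be a mistake to infer any effect on the trial's inference: the bDFS endpoint, the sample sizes of 32 and 40, and the planned analyses do not use these rules.

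**What to change.** Amend Section 8 as follows.

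1. **Key 8.5.6 to each course's final fraction.** Boost: carry-over on fractions 1-2, final-fraction rule on fraction 3. Monotherapy: carry-over on fractions 1-4, final-fraction rule on fraction 5. State that stopping at 90% forgoes only the remainder of that final fraction.
2. **State the denominator.** Say that the tolerance of under 5% BED for the boost is of boost plus IMRT.
3. **State which PTV limit governs.** Keeping the 130% cap means a table with normalization of 77-80% and upper maxima of 27.3 / 47.1 Gy. If the sponsor prefers the table, the cap in 8.4.4.1 must be restated to match; that is a clinical decision.
4. **Correct Section 8.1** to 36.25 Gy (7.25 Gy x 5).

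The cost is a short amendment with no new data. A 77% floor narrows planning freedom, whereas a higher cap accepts hotter spots. Some plans already delivered may need to be recorded as variations. Giving a final-fraction deficit on a separate day still lowers BED somewhat, but the existing branch for less than 2/3 already accepts that.
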